Each period will be of 3 days duration. It is anticipated that Study Periods 1, 2, 3, and 4 will commence on Study Days 1, 4, 7, and 10, respectively. For logistical reasons, the interval between periods may be extended by up to 2 days to accommodate site schedules. The minimum washout between periods is 3 days.

Screening (Visit 1) will include procedures to access subject eligibility including clinical laboratory tests, physical examination, and driving simulation training/screening. Prior to randomization, subjects will be screened for simulator sickness and will receive standardized training on the driving simulator and cognitive test battery. Screening procedures and screening assessments may be performed on different days but must be completed within 28 days before Period 1 (Visit 2). The training drives on the driving simulator must be completed no more than 21 days prior to the first dose of study drug.

Study drug or placebo will be administered by site staff during each period at 0 (Dose 1), 6 (Dose 2), and 10 (Dose 3) hours on Day 1 and at 22 hours (Dose 4) on Day 2 according to the treatment sequence assigned. Subjects will wear a blindfold when taking each dose to maintain the blind. The tablet size and shape are deemed similar enough to maintain the blind provided the subject is blindfolded. Driving assessments commence at 8, 12, and 24 hours after Dose 1.

The positive control (diphenhydramine 50 mg) is included to establish the sensitivity of the study endpoints.

Treatment Arms:

Treatment Sequences:

Subjects will be assigned and dosed with study medication (lasmiditan, diphenhydramine, or placebo) according to the treatment sequence they are randomized to. Subjects will be randomized equally into 1 of 4 treatment sequences:

Treatment Sequence	Period 1	Period 2	Period 3	Period 4
1	Placebo	Lasmiditan 100 mg	Diphenhydramine 50 mg	Lasmiditan 200 mg
2	Lasmiditan 100 mg	Lasmiditan 200 mg	Placebo	Diphenhydramine 50 mg
3	Lasmiditan 200 mg	Diphenhydramine 50 mg	Lasmiditan 100 mg	Placebo
4	Diphenhydramine 50 mg	Placebo	Lasmiditan 200 mg	Lasmiditan 100 mg

Duration of Study:

On Day -1, prior to the first dose administration (the evening of clinical research unit [CRU] admission) subjects will complete a 20-minute practice drive on the CRCDS-MiniSim and a practice trial on the CogScreen SDC test.

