		Lasmiditan and Metabolites PK Sample ^a
		Study Drug Administration (Dose 2)
+8.0 h		
		KSS ^b
		Adverse Event Assessment ^b
		CogScreen SDC Test ^b
		Self-Perceived Questionnaire (safe to drive)
		Lasmiditan and Metabolites PK Sample ^a
		Diphenhydramine PK Sample ^a
		CVDA Drive
		VAS (immediately after drive)
+10.0 h		
		Lasmiditan and Metabolites PK Sample ^a
		Study Drug Administration (Dose 3)
+11.0 h		Dinner
+12.0 h		
		KSS ^b
		Adverse Event Assessment ^b
		CogScreen SDC Test ^b
		Self-Perceived Questionnaire (safe to drive)
		Lasmiditan and Metabolites PK Sample ^a
		Diphenhydramine PK Sample ^a
		CVDA Drive
		VAS (immediately after drive)
Day 2 (Periods 1-4)	+22 h	Study Drug Administration (Dose 4)
	+23 h	Breakfast
	+24 h	
		KSS ^b
		Adverse Event Assessment ^b
		CogScreen SDC Test ^b
		Self-Perceived Questionnaire (safe to drive)
		Lasmiditan and Metabolites PK Sample ^a
		Diphenhydramine PK Sample ^a
		CVDA Drive
		VAS (immediately after drive)
	+36 h	Lasmiditan and Metabolites PK Sample ^a
Day 3 (Periods 1-4)	+48 h	Lasmiditan and Metabolites PK Sample ^a
Discharge (Day 3, Period 4)	Discharge from Clinical Unit	
		Vital Signs
		Physical Examination
		Clinical Laboratory Tests
		Adverse Event Assessment
		Concomitant Medication Assessment
Early Discontinuation		
		Vital Signs

		Physical Examination
		Clinical Laboratory Tests
		Twelve-Lead ECG
		Urinalysis Samples
		Serum Pregnancy Test (females only)
		Adverse Event Assessment
		Concomitant Medication assessment
Within 5 to 9 days after Discharge	Follow-up	
		Vital Signs
		Physical Examination
		Clinical Laboratory Tests
		Twelve-Lead ECG
		Urinalysis Samples
		Serum Pregnancy Test (females only)
		Adverse Event Assessment
		Concomitant Medication Assessment

Abbreviations: BMI = body mass index; CVDA = Country Vigilance-Divided Attention; ECG = electrocardiogram; h = hours, KSS = Karolinska Sleepiness Scale; PK = pharmacokinetic; SDC = Symbol Digit Coding; VAS = Visual Analog Scale.

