- a Pharmacokinetic and pharmacodynamic sampling times are given as targets to be achieved within reasonable limits. For PK sampling scheduled prior to driving assessments, the sampling window should be within -5 min to avoid conflict with driving assessment. Otherwise, the standard PK sampling windows: predose: -15 minutes; >0 to 2 hours postdose: ±5 minutes; 2.5 to 6 hours postdose: ±10 minutes; 7 to 12 hours postdose: ±20 minutes; >12 hours postdose: ±30 minutes. The samples will be taken as per schedule to maintain the blind but samples will be analyzed according to the randomization table.
- b This accompanying driving assessment procedure should occur within -30 minutes before the scheduled CVDA drive targeted for this sampling time

3. Introduction

Lasmiditan is being developed by Eli Lilly and Company (Lilly) for the acute treatment of migraine attacks with or without aura in adults. This molecule has been developed by Lilly as LY573144 and by CoLucid Pharmaceuticals, Inc. as COL-144 under the Investigational New Drug application 103420. Full details of lasmiditan's preclinical and clinical safety and tolerability information are contained in the Investigator's Brochure (IB).

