3.2. Background

Lasmiditan is being investigated for the acute treatment of migraine in adults with and without aura. Lasmiditan is a high-affinity, highly selective 5-HT (serotonin)_{1F} receptor agonist that is being developed as a novel therapy for the acute treatment of migraine. It has a chemical structure and pharmacologic profile that is distinct from the triptans, the current standard of care for the treatment of acute migraine. Lasmiditan does not contain the indole group observed in all triptans; instead it has a pyridinoyl-piperidine scaffold, which is unique to antimigraine medications. Lasmiditan is a low-molecular weight 5-HT_{1F} receptor agonist with a nonvascular, primarily neural mechanism of action. It has high affinity for the human 5-HT_{1F} receptor and >470-fold selectivity for the human 5-HT_{1F} receptor relative to the 5-HT_{1B} receptor. Across the completed Phase 1, 2, and 3 clinical studies, lasmiditan doses of 0.1 mg to 400 mg were evaluated in healthy subjects or patients with migraine. In two Phase 3, placebo-controlled studies in which patients treated 1 migraine attack with oral lasmiditan (50, 100, or 200 mg) or placebo, the most frequently reported lasmiditan treatment-emergent adverse events (TEAEs) were dizziness, paresthesia, somnolence, fatigue, lethargy, and nausea. A majority of these TEAEs were mild or moderate in severity. In healthy subjects, peak plasma concentrations of lasmiditan were observed approximately 1.5 hours to 2.5 hours after a single oral dose ranging from 25 mg to 400 mg, and the geometric mean terminal half-life was approximately 4 hours. Lasmiditan pharmacokinetics (PK) was approximately dose linear.

Following oral dosing with lasmiditan, up to 11 metabolites, including 3 major metabolites (M7, M8, and M18), were detected in human plasma and urine. These metabolites lacked significant pharmacological activity at the 5 HT_{1F} receptor and were generally considered to be pharmacologically inactive. The relative proportions of metabolites to intact lasmiditan

remained reasonably constant throughout the oral dose range studied and their PK was approximately linear. The half-life of the metabolites ranged from ~4.5 hours to 21 hours.

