9.4.2. Vital Signs

For each subject, vital sign measurements should be conducted according to the Schedule of Activities (Section 2).

Blood pressure and pulse rate should be measured singly after at least 5 minutes supine. For each individual subject, the same cuff size should be used throughout the study for the measurements of BP. The cuff should be attached to the subject's dominant arm.

Unscheduled orthostatic vital signs should be assessed, if possible, during any AE of dizziness or posture-induced symptoms. Where orthostatic measurements are required, subjects should be supine for at least 5 minutes and then subjects will stand, and standing BP will be measured after

2 minutes; no longer than 3 minutes. If the subject feels unable to stand, supine vital signs only will be collected.

Additional vital signs may be measured during each study period if warranted.

9.4.3. *Electrocardiograms*

For each subject, ECGs should be collected according to the Schedule of Activities (Section 2).

Any clinically significant findings from ECGs that result in a diagnosis and that occur after the subject receives the first dose of the investigational product should be reported to Lilly, or its designee, as an AE via eCRF.

For each subject, a single 12-lead digital ECG will be collected according to the Schedule of Activities (Section 2). Electrocardiograms must be recorded before collecting any blood samples. Subjects must be supine for approximately 5 to 10 minutes before ECG collection and remain supine but awake during ECG collection. Electrocardiograms may be obtained at additional times, when deemed clinically necessary. All ECGs recorded should be stored at the investigative site.

Electrocardiograms will be interpreted by a qualified physician (the investigator or qualified designee) at the site as soon after the time of ECG collection as possible, and ideally while the subject is still present, to determine whether the subject meets entry criteria at the relevant visit(s) and for immediate subject management, should any clinically relevant findings be identified.

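### The first scheduled postdose AE assessment comes 5.0–6.5 h after the lasmiditan peak but 1.5–2 h after diphenhydramine doses, and in Periods 1–3 none is scheduled between 24 h and about 8 h of the next period

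*Protocol*

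**What the plan says.** The Schedule of Activities (protocol Section 2) lists an AE assessment on Day -1 of Period 1. In every period it then lists one at +8, +12 and +24 h after Dose 1. Each of these carries footnote b ("Adverse Event Assessment ^b"), which sets the timing: "This accompanying driving assessment procedure should occur within -30 minutes before the scheduled CVDA drive targeted for this sampling time". The remaining ones are at discharge on Day 3 of Period 4, at early discontinuation and at follow-up. None is listed at Day 1 predose, between Dose 1 and the 8 h drive, at +36 h, or at +48 h in Periods 1–3.

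Section 3.2 states that "peak plasma concentrations of lasmiditan were observed approximately 1.5 hours to 2.5 hours after a single oral dose" and that "the geometric mean terminal half-life was approximately 4 hours". It names dizziness, paresthesia, somnolence, fatigue, lethargy and nausea as the commonest events in Phase 3. Sections 3.1 and 5.4 place the diphenhydramine doses 2 h before each drive.

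On spacing, the synopsis and Section 5.4 say that "Study Periods 1, 2, 3, and 4 will commence on Study Days 1, 4, 7, and 10, respectively", and that "the interval between periods may be extended by up to 2 days to accommodate site schedules".

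Other parts of the protocol cover AEs outside the scheduled enquiries. Subjects are monitored in the unit throughout (Section 3.3), and AEs are recorded from consent onward (Sections 9.2 and 9.2.1). For dizziness, Section 9.4.2 says: "Unscheduled orthostatic vital signs should be assessed, if possible, during any AE of dizziness or posture-induced symptoms". SAP Section 9.6.1 tabulates treatment-emergent AEs by treatment, severity, relationship, system organ class and preferred term.

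**The concern.** The common lasmiditan events are mostly subjective symptoms, and how many are recorded depends partly on whether and when someone asks. The schedule fixes the asking to the drives. That suits the control, which is dosed shortly before each drive, but not lasmiditan, whose plasma peak is several hours earlier. A by-treatment AE table would then compare treatments enquired about at different points after dosing. Blinding does not remove this, because it is built into the timetable.

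The second issue is the long stretch without an enquiry after 24 h in Periods 1–3. An event in that stretch that the subject does not volunteer is first asked about after the next treatment has been given, so its treatment column then depends on a recalled onset. The SAP defines treatment-emergence by occurrence relative to dosing, but gives no explicit rule for assigning an event to one of the four periods.

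What is at stake is the quality of the safety description. The driving endpoint is not involved.

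**Working it through.** The plan states no figure on this point, so the check is arithmetic on nominal schedule times.

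**Inputs**
- AE assessments at 8, 12 and 24 h, each 0–30 min before the drive (Section 2, footnote b): windows 7.5–8, 11.5–12 and 23.5–24 h.
- Lasmiditan peak at 1.5–2.5 h, half-life about 4 h (Section 3.2). Lasmiditan is taken to be given at Dose 1: it is a single dose (Section 5.1), and the drives are set at 8, 12 and 24 h both after lasmiditan (Section 3.1) and after Dose 1 (synopsis).
- Diphenhydramine at 6, 10 and 22 h (synopsis dose times; 2 h before each drive, Section 5.4).
- Dose 1 to Dose 1: Days 1, 4, 7 and 10, so 72 h; with the 2-day extension, 72 + 48 = 120 h.

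**Lag of the first enquiry behind the lasmiditan peak**
- Shortest: 7.5 − 2.5 = 5.0 h. Longest: 8 − 1.5 = 6.5 h.
- In half-lives: 5.0/4 = 1.25 to 6.5/4 = 1.6.
- Share of the peak concentration left, assuming mono-exponential decline from the peak: 2^(−5.0/4) = 0.42 to 2^(−6.5/4) = 0.32.

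**Enquiry relative to diphenhydramine doses**
- 7.5 − 6 = 1.5 h to 8 − 6 = 2 h. The same 1.5–2 h applies after the doses at 10 h (11.5–12 h) and 22 h (23.5–24 h).

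**Gap from the 24 h assessment to the next period's first one (Periods 1–3)**
- Usual spacing: 72 + 7.5 − 24 = 55.5 h to 72 + 8 − 23.5 = 56.5 h.
- With the 2-day extension: 120 + 7.5 − 24 = 103.5 h to 120 + 8 − 23.5 = 104.5 h.
- Each treatment falls in Periods 1–3 in three of the four sequences (Table LAIF.3), so the gap applies to each treatment in three sequences. In the fourth sequence that treatment is in Period 4. The next assessment is then at discharge on Day 3, about 48 − 24 = 24 h to 48 − 23.5 = 24.5 h later if discharge is at about 48 h.

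**Contacts already in the schedule**
- Blood draws at 0.5, 1, 1.5, 2, 3 and 4 h, with vital signs at +2 and +4 h.
- A blood draw at +48 h.
- At predose: vital signs, a symptom-directed examination and blood draws.

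**With questions added at +2, +4, +48 h and predose (nominal times)**
- The first enquiry is at 2.0 h, within 0.5 h of the expected peak on either side.
- The gap after 24 h falls to 24–24.5 h. From +48 h to the next predose is 72 − 48 = 24 h, or 120 − 48 = 72 h with the extension.
- No interval between enquiries then spans a change of treatment unquestioned, because the predose enquiry comes before the new dose.

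**The case against.** The strongest reply is that a scheduled line is not the only way an AE reaches the database. Subjects live in the unit, staff see them six times between 0.5 and 4 h, and AEs are recorded from consent without reference to schedule lines. This stands. A reader might infer that peak CNS events rest on recall. The documents do not support that: an event volunteered or observed at 2 h is recorded at 2 h. What is missing is a prompt. Section 9 points to Section 2 for procedures and their timing. There the concomitant medication line is marked for monitoring throughout and the AE line is not, so each site of a multicenter trial is left to decide whether to ask.

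Further points on that side also stand:
- **Treatment attribution.** A reader might infer that the SAP assigns late events to the wrong treatment. It does not: SAP Section 9.6.1 goes by when the event occurs, and Section 7.2.1 has actual dose times recorded. For lasmiditan, 24 h is already (24 − 2.5)/4 = 5.4 to (24 − 1.5)/4 = 5.6 half-lives past the peak, and Section 3.2 regards its metabolites as generally inactive, so a new late event is unlikely. Diphenhydramine Dose 4 at 22 h is a closer case, with only one scheduled enquiry before the gap.
- **Onset and duration.** No summary of either is planned, so no specified output is distorted in that respect.
- **Orthostatic readings.** These are unscheduled, event-triggered and required only if possible. They do not depend on the 8 h enquiry, although dizziness that has resolved before it is first mentioned cannot be measured.
- **Predose examination.** It is symptom-directed, so someone may well ask about symptoms then. No AE enquiry is listed, however.
- **Early driving test.** Section 3.1 deliberately leaves the 90-minute test to the earlier study. That explains the missing drive, but not the missing AE question.

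**Conclusion.** The point holds as a modest, inexpensive improvement to safety ascertainment. The first scheduled postdose enquiry comes 5.0–6.5 h after the expected lasmiditan peak, against 1.5–2 h after each diphenhydramine dose. In Periods 1–3 a gap of 55.5–56.5 h (103.5–104.5 h if extended) spans a change of treatment. Period 4 does not share this gap, since it has discharge and follow-up assessments.

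These figures rest on nominal times and the peak range in Section 3.2. The 32–42% of peak concentration remaining also assumes mono-exponential decline with a 4 h half-life. The documents give no basis for estimating how many events would go unrecorded, so no under-recording rate is claimed.

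A reader might also infer that the trial's conclusion on duration of effect is weakened. It is not. SDLP, the sleepiness scale and the coding test are measured at 8, 12 and 24 h regardless of AE enquiry, and the SAP plans no inferential safety analysis (Section 9.6.9).

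**What to change.** Add a non-leading AE assessment to the Schedule of Activities in every period at contacts that already exist:
- +2.0 h and +4.0 h, with the vital signs and blood draw;
- +48 h, with the blood draw (in Period 4 this may coincide with the discharge assessment);
- Day 1 predose of Periods 2–4, before Dose 1, with the vital signs.

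The schedule stays identical across treatments, so the blind is not affected.

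In SAP Section 9.6.1, state that each event is assigned to a treatment by its recorded onset relative to actual dose times. An event with onset before Dose 1 of Period 2, 3 or 4 then counts under the preceding treatment.

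The cost is four added lines in the schedule and eCRF and a little staff time, with no new visit or sample. More mild AEs will be recorded, possibly more in the lasmiditan periods, since the +2 h and +4 h questions fall nearest the lasmiditan peak.

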3.1. Study Rationale

Lasmiditan is a highly selective and potent agonist at the 5-hydroxytryptamine (5-HT)_{1F} receptor and is under development as a neurally acting treatment for migraine. The most frequently reported adverse events (AEs) identified in the lasmiditan clinical development program are central nervous system (CNS) in nature based on the mechanism of action of the drug. Due to treatment-related adverse effects of dizziness and fatigue observed in the Phase 2 clinical program, Study COL-MIG-106/H8H-MC-LAHG (106/LAHG) evaluating the impact of lasmiditan on driving performance was conducted in accordance with the United States Food and Drug Administration (FDA)'s Evaluating Drug Effects on the Ability to Operate a Motor Vehicle: Guidance for Industry (2017)

Study 106/LAHG was a randomized, subject-and investigator-blind, placebo-controlled, five-period, crossover study with the following treatments:

- Lasmiditan 50 mg
- Lasmiditan 100 mg
- Lasmiditan 200 mg
- Alprazolam 1 mg (positive control)
- Placebo

Subjects were randomized equally into 1 of 10 Latin square treatment sequences. The five periods were approximately 7 days in duration.

Period 1 → Washout 1 → Period 2 → Washout 2 → Period 3 → Washout 3 → Period 4 → Washout 4 → Period 5 → EOS
Day 1 Days 2-6 Day 7 Days 8-13 Day 14 Days 15-20 Day 21 Days 22-27 Day 28 Day 35

The simulated driving test was commenced 90 minutes after dosing (on Days 1, 7, 14, 21, and 28).

The effect of lasmiditan on simulated driving performance was primarily measured by the standard deviation of lateral position (SDLP) using the Cognitive Research Corporation Driving Simulator (CRCDS)-MiniSim. During testing, subjects were instructed to drive a 100-km highway segment with steady lane position and constant speed with a primary outcome measure of vehicle control, the SDLP (i.e. amount of "weaving" of the car in the lane).

Driving performance as assessed by SDLP was inferior for lasmiditan 50 mg, 100 mg, and 200 mg relative to placebo. This was further confirmed by symmetry analysis. A majority of

subjects exceeded the impairment threshold (4.4 cm, comparable to 0.05% blood alcohol count [BAC]) at even the lowest dose of lasmiditan. Sensitivity of the simulator and the model used in the research design were supported by significant findings on primary and secondary driving endpoints for alprazolam 1.0 mg.

Secondary driving endpoints provide further support to the conclusion that lasmiditan 50 mg, 100 mg, and 200 mg at 1.5 hours postdose had an adverse impact on simulated driving performance.

The time interval in 106/LAHG was chosen to capture the effect at the time of the peak concentration of lasmiditan and major metabolites M7 and M8, in accordance with the FDA guidance. However, the point at which patients should resume operation of a motor vehicle after taking lasmiditan is still unclear. The primary objective in the current study is to determine the duration of effect of lasmiditan compared to placebo on simulated driving performance in healthy subjects as measured by SDLP using the CRCDS-MiniSim at 8, 12, and 24 hours after dosing with lasmiditan. The 90-minute postdose simulated driving assessment used in 106/LAHG will not be repeated in the current study. For the positive control, diphenhydramine treatment doses will be administered 2 hours prior to driving assessments to ensure the maximum cognitive and sedative effect of the positive control (Ramaekers and O'Hanlon 1994).

3.2. Background

Lasmiditan is being investigated for the acute treatment of migraine in adults with and without aura. Lasmiditan is a high-affinity, highly selective 5-HT (serotonin)_{1F} receptor agonist that is being developed as a novel therapy for the acute treatment of migraine. It has a chemical structure and pharmacologic profile that is distinct from the triptans, the current standard of care for the treatment of acute migraine. Lasmiditan does not contain the indole group observed in all triptans; instead it has a pyridinoyl-piperidine scaffold, which is unique to antimigraine medications. Lasmiditan is a low-molecular weight 5-HT_{1F} receptor agonist with a nonvascular, primarily neural mechanism of action. It has high affinity for the human 5-HT_{1F} receptor and >470-fold selectivity for the human 5-HT_{1F} receptor relative to the 5-HT_{1B} receptor. Across the completed Phase 1, 2, and 3 clinical studies, lasmiditan doses of 0.1 mg to 400 mg were evaluated in healthy subjects or patients with migraine. In two Phase 3, placebo-controlled studies in which patients treated 1 migraine attack with oral lasmiditan (50, 100, or 200 mg) or placebo, the most frequently reported lasmiditan treatment-emergent adverse events (TEAEs) were dizziness, paresthesia, somnolence, fatigue, lethargy, and nausea. A majority of these TEAEs were mild or moderate in severity. In healthy subjects, peak plasma concentrations of lasmiditan were observed approximately 1.5 hours to 2.5 hours after a single oral dose ranging from 25 mg to 400 mg, and the geometric mean terminal half-life was approximately 4 hours. Lasmiditan pharmacokinetics (PK) was approximately dose linear.

Following oral dosing with lasmiditan, up to 11 metabolites, including 3 major metabolites (M7, M8, and M18), were detected in human plasma and urine. These metabolites lacked significant pharmacological activity at the 5 HT_{1F} receptor and were generally considered to be pharmacologically inactive. The relative proportions of metabolites to intact lasmiditan

remained reasonably constant throughout the oral dose range studied and their PK was approximately linear. The half-life of the metabolites ranged from ~4.5 hours to 21 hours.

